Acceptability will be evaluated using the method proposed by Ahn et al. (2019) (29). Participants and/or their caretakers will be asked to apply a Likert scale (from 0 [strongly disagree] to 10 [strongly agree]) to answer ten affirmatives regarding the use of home-based tDCS. For example, question 1: "It was easy to prepare the device and accessories", question 7: "I felt confident using the device." Overall acceptability across groups will be evaluated by descriptive measures of satisfaction ratings. GLM will model participant satisfaction ratings as a function of treatment group (active vs. sham tDCS). We expect that participant satisfaction ratings at the end of treatment will demonstrate high acceptance of tDCS treatment in the present sample.

Safety will be assessed with a questionnaire about side effects that include itching, burning, headache, fatigue, and dizziness (29). Descriptive statistics will describe raw frequencies of AEs and side effects. Treatment group differences in AEs and side effects will be evaluated via Chi-square and Fisher's exact test of contingency tables. We expect that adverse events and side effects will be rare, and any that may occur will be mild.

The primary clinical outcome measure will be change on the Apathy Evaluation Scale score (42), the best-validated scale for measuring apathy in AD, which consists of 18 items phrased as questions that are to be answered by the caregiver on a four-point Likert scale, with higher scores indicating greater severity of apathy. Apathy will be

assessed at baseline, during treatment (weeks 2, 4 and 6) and 6 weeks post-treatment. Our hypothesis is that active tDCS group will demonstrate lower apathy scores at the end of treatment relative to sham tDCS. GLM will evaluate residual change by modeling apathy at the end of treatment as a function of treatment group, controlling for apathy at the beginning of treatment. This analysis is a regression-based analogue to ANCOVA that permits non-normally distributed outcome distributions. Follow-up analyses will evaluate change over time across groups via GLM with multilevel components (GLMM) as well as cross-sectional analyses within each measurement time point via GLM.

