The secondary clinical outcome measures will include: (1) total score on the Brief Dimensional Apathy Scale (bDAS) (43); (2) total score on the NPI-Q which evaluates 12 discrete NPS considering their severity and the related caregiver distress (38-40); (3) depressive symptoms as assessed by the Cornell Scale for Depression in Dementia (41); (4) cognition as evaluated by the Mini-Mental State Examination (MMSE), which includes memory, language, praxis and orientation tasks, yielding a global cognition score ranging 0 to 30, with higher scores indicating better performance (35).

Our hypothesis is that active tDCS group will demonstrate lower scores on the bDAS, NPI-Q and Cornell Scale for Depression, and higher scores on the MMSE at the end of treatment relative to sham tDCS. GLM will evaluate residual change in each outcome (in separate models) by modeling scores at the end of treatment as a function of treatment group, controlling for baseline.

Sociodemographic data (gender, age, marital status and education) will be collected at the baseline. Clinical (health history, use of medication and life habits) and anthropometric data will be collected at the baseline and after the treatment period. These data will be control variables for the study.

Table 1. Timetable for Collection of Data

Assessment	Baseline	Week 2	Week 4	Week 6	Week 12
Medical History Questionnaire	X				
MMSE	X			X	X
AES (primary outcome)	X	X	X	X	X
NPI-Q	X	X	X	X	X
bDAS	X	X	X	X	X
Cornell Scale for Depression	X			X	X
tDCS experience questionnaire		X	X	X	X
Side effects questionnaire		X	X	X	X

Data and Safety Monitoring

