Descriptive statistics will evaluate measures of central tendency and frequencies for all continuous and categorical variables (respectively) measured in the study. Correlation analyses (i.e., Pearson's r , Spearman's ρ) will be used to evaluate broad patterns of relationships across variables. Preliminary data analyses will inspect relationships between sample characteristics (e.g., demographics), experimental group (e.g., active vs. sham tDCS), and specified outcome variables (e.g., Apathy) via traditional statistical tests (e.g., chi-square; Mann-Whitney; t -tests). Any sample characteristic variables that demonstrate a relationship with both predictor and outcome variables in a given model meet criteria for being a potential confounder (32, 33) and will be included as a covariate in such models for hypothesis testing.

Statistical modeling will primarily use generalized linear modeling (GLM) with multilevel components (GLMM) for correlated observations. Potentially nonlinear relationships between predictors and outcomes will be evaluated via inclusion of polynomial or spline effects. Continuous, dichotomous, and count-distributed data will utilize linear, logistic, and Poisson/negative binomial regression, respectively (each with a canonical link function). Evaluation of distributional assumptions will use residual plots, formal statistical tests, and posterior predictive checking. Violations of assumptions will be addressed via transformation, robust estimation, stratification, and/or coefficient scaling where appropriate. Statistical analyses will be performed using the R statistical computing environment via packages lme, rstan, and brms.

Missing data will be addressed via maximum likelihood, explicit modeling of missingness, or imputation where appropriate. Each approach is robust to ignorable missingness (i.e. MCAR and MAR). Sensitivity analyses will permit evaluation of the robustness of findings to missing data assumptions. While Bayesian analyses are not influenced by traditional concerns of multiplicity, for the frequentist analyses, all primary outcome variables (those specified by name in the hypothesis statements) will be evaluated at the $\alpha = 0.05$ statistical significance level, while any secondary or otherwise post hoc analyses will employ false discovery rate (FDR) to control for Type I error.

Ethics/Protection of Patient Confidentiality

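### The week-6 apathy test does not use the week 2 and week 4 scores, so the plan's claim of robustness to MAR is not true in general for that model

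*Combined protocol and SAP*

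**What the plan says.** Study Procedures gives the model for the primary clinical outcome: "GLM will evaluate residual change by modeling apathy at the end of treatment as a function of treatment group", with AES at the start of treatment as covariate. The AES is "assessed at baseline, during treatment (weeks 2, 4 and 6) and 6 weeks post-treatment", and Table 1 confirms five visits. The scores at weeks 2 and 4 are named only for follow-up analyses: a multilevel model of change over time, and separate analyses at each visit.

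Baseline terms may be added. Sample characteristics related to both arm and outcome "will be included as a covariate in such models for hypothesis testing" (Statistics, repeated under Study Design). Sociodemographic, clinical and anthropometric data are described thus: "These data will be control variables for the study". No post-baseline AES score is named as a term in the hypothesis test.

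On missing data, Statistics says: "Missing data will be addressed via maximum likelihood, explicit modeling of missingness, or imputation where appropriate. Each approach is robust to ignorable missingness", which it spells out as MCAR and MAR. The next sentence promises sensitivity analyses to missing-data assumptions without describing them. No approach is tied to the week-6 AES model and no imputation variables are listed.

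The secondary clinical outcomes follow the same pattern: "GLM will evaluate residual change in each outcome (in separate models) by modeling scores at the end of treatment". Of these, Table 1 collects bDAS and NPI-Q at weeks 2 and 4. MMSE and the Cornell scale have no visit between baseline and week 6.

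**The concern.** A person who leaves after week 4 has two on-treatment AES scores. These are the observed values most likely to predict both leaving and the missing week-6 score. If leaving depends on them, the mechanism is MAR given everything collected. It is not ignorable for a model that contains only arm, baseline AES and other baseline variables.

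If the dependence also differs by arm, the week-6 contrast is biased although the data that would remove the bias are in hand. For example, sham participants might leave because apathy is not improving, while active participants leave for other reasons. The plan treats differential completion as possible, since Study Procedures compares completion between groups. The Bayesian analysis, which provides the main inference, has the same gap if it fits the same regression.

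**Working it through.** **The plan's own figure.** Statistics gives 80% power at N = 40, alpha 0.05, f = 0.45 for the residual-change model. ANCOVA F test with one covariate: df = 1 and 40 − 2 − 1 = 37, noncentrality f²N = 0.2025 × 40 = 8.1, power 79.1%. The figure reproduces. For two equal arms f = 0.45 is d = 0.90 residual SD. With 28 completers (70% of 40) the noncentrality is 0.2025 × 28 = 5.67 on 1 and 25 df, and power is 62.9%.

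**Why maximum likelihood is complete case here.** Write A for arm, Y0 and Y6 for AES at baseline and week 6, and R for having Y6. A person with Y6 contributes f(Y6 | A, Y0). A person without it contributes the integral of that density over Y6, which is 1. Dropouts therefore add nothing. The fit is valid if R is independent of Y6 given A, Y0 and any other modelled baseline variables. If R depends on week-4 AES, and week-4 AES predicts Y6 beyond those variables, the condition fails.

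**Size.** None of the following assumptions is in the documents: normal AES with SD 1; correlation 0.5 or 0.7 at every lag, or 0.8 between adjacent visits (AR(1)); 30% missing at week 6, with weeks 2 and 4 seen for all; a true week-6 effect of 0 or −0.90 SD that builds linearly; logistic dropout with log-odds slope 1.2 per SD of week-4 AES. Each scenario used 400,000 people. Bias is the complete-case estimate minus the full-data estimate. A negative effect favours active, so positive bias works against it.

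| Dropout depends on | Bias, true effect 0 (corr. 0.5 / 0.7 / AR 0.8) | Bias, true effect −0.90 |
|---|---|---|
| arm and baseline AES | 0.000 / −0.001 / −0.003 | −0.005 / −0.002 / −0.003 |
| week-4 AES, same rule in both arms | 0.001 / −0.001 / −0.002 | 0.028 / 0.023 / 0.053 |
| week-4 AES, sham only | 0.080 / 0.065 / 0.147 | 0.081 / 0.069 / 0.149 |
| week-4 AES, active only | −0.081 / −0.065 / −0.148 | −0.064 / −0.055 / −0.119 |
| week-4 AES, opposite by arm | 0.150 / 0.129 / 0.293 | 0.149 / 0.130 / 0.289 |

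An estimator that also used weeks 2 and 4 returned the full-data value within 0.005 SD in every row. Imputing from arm and baseline alone gave exactly the complete-case estimate.

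**At the planned size.** A separate simulation used 4,000 trials of 20 per arm, with assumed AES SD 9, a 6-point effect, 27–30% missing, and dropout driven by the last observed AES. Complete-case bias was 1.12–1.45 points with sham-only dependence (÷ 9 = 0.12–0.16 SD), 2.01–2.62 points with opposite dependence (0.22–0.29 SD), 0.27–0.43 points with a common rule (0.03–0.05 SD), and 0 with random dropout. Likelihood using all visits had bias of at most 0.08 points. Under random dropout the complete-case variance was 9–13% higher.

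**Scale against the decision rule.** With 14 completers per arm the standard error is √(2/14) = 0.378 residual SD. Multiplied by √(1 − r²), that is 0.327 total SD at r = 0.5 and 0.270 at r = 0.7. With a near-flat prior, a posterior probability of 0.75 needs an estimate of 0.674 standard errors, or 0.18–0.22 SD. Under AR(1) 0.8 the baseline to week-6 correlation is 0.8³ = 0.512 and the standard error is 0.325. A bias of 0.15 is then 0.15/0.325 = 0.46 standard errors. With no true effect, it raises the chance of reaching 0.75 in the direction of the bias from 25% to about 1 − Φ(0.674 − 0.46) = 42%.

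**The case against.** A reader might infer that the plan documents a complete-case analysis, that its robustness sentence is simply false, that the interim scores are thrown away, and that the model holds nothing but arm and baseline AES. The documents support none of these as stated.

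- The plan lists three approaches and ties none of them to this model. Imputation that includes weeks 2 and 4 would be valid and is permitted.
- Complete-case likelihood is itself valid when dropout depends only on arm and modelled baseline variables.
- The follow-up multilevel model uses the interim scores, and missing-data sensitivity analyses are promised.
- Baseline covariates may join the model, although they do not bring in the week 2 and 4 scores.

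The size also depends on the mechanism. The larger figures need dropout that tracks AES differently by arm. Even then the one-arm bias is at most about half a standard error. Thirty percent is a ceiling, because the expectation above 70% concerns completing a study that runs to week 12, and the plan elsewhere anticipates high retention. Efficacy is the secondary goal.

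These points narrow the claim without removing it. Leaving the choice to what seems appropriate later does not assign a valid method to the hypothesis test. Two natural readings, likelihood on the stated model and imputation from its own covariates, give the complete-case answer. The multilevel model's week-6 contrast is not the hypothesis test.

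**Conclusion.** The concern holds in limited form. The plan's MAR statement is not true in general for the week-6 AES regression. It fails for likelihood on that model, and for imputation from arm and baseline alone, when dropout depends on week 2 or 4 AES. At 30% missing, the bias is about 0.06–0.15 SD if the dependence is in one arm and 0.13–0.29 SD if it runs in opposite directions. It is at most about 0.05 SD under a common rule with a true effect, and essentially nil under a common rule with no effect or under random dropout. The direction cannot be known in advance. These sizes rest on assumed correlations and dropout rules, and lower week-6 missingness would generally reduce them. The primary feasibility, acceptability and safety goals are unaffected.

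**What to change.** Choose one of two routes and state it in the SAP for both the Bayesian and the frequentist analysis.

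1. Take the week-6 AES contrast from the longitudinal model already planned, with categorical visit, arm-by-visit interaction, baseline AES as covariate, and a covariance structure feasible at N = 40. Pre-specify a simpler fallback: an unstructured covariance over four post-baseline visits has 4 × 5 / 2 = 10 parameters.
2. Keep the ANCOVA-type GLM and pre-specify multiple imputation of week-6 AES from arm, baseline, week 2 and week 4 AES. Entering arm as a term avoids separate imputation models on about 14 completers each. This route also keeps the planned GLM if non-normality is the worry.

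Keep the complete-case ANCOVA as a sensitivity analysis. Limit the MAR sentence to analyses that use the interim scores. Do the same for bDAS and NPI-Q.

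The cost is SAP wording and a slightly larger model, since the data and the multilevel model are already planned. Neither route helps for people who leave before week 2, beyond their baseline score, or protects against dropout that depends on the unseen week-6 score. The promised sensitivity analyses should address the latter.

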We will carry out a randomized, experimenter- and participant-blinded trial comparing home-based active tDCS and home-based sham tDCS. Participants will be randomized 1:1 to either treatment condition. Half of the participants (n=20) will receive active (constant current intensity of 2mA), while half (n=20) will receive sham tDCS. No changes to the patient's standard care medication will be made. Participants will continue to receive standard treatment for their individual health problems. **Anode and cathode electrodes will be placed over the left and right dorsolateral prefrontal cortices, respectively, with the use of the Omni-Lateral-Electrode system.** Caregivers will set up and administer tDCS for participants with ADRD at home. tDCS will be applied for 30 min at an intensity of 2mA, with 30 s ramping up and down. The same procedure will be used for sham stimulation, but in this case, electric current will be applied only in the first 30s tDCS. All patients, caregivers and clinicians will be blinded to the type of stimulation delivered. We will use bi-hemispheric stimulation (anode F3/cathode F4) based on the facts that bilateral frontal circuits have been implicated in apathy, and bilateral stimulation may have wider effects on brain networks (18, 23, 26). The stimulation will last 30 min according to previous studies (17, 23, 27). According to our previous home-based tDCS protocols (28, 29), all sessions will be remotely supervised by trained research staff (RA), therefore, the sessions will run from Monday to Friday. The remote supervision of the sessions will be possible through video conferencing software (e.g., WebEx), and will ensure the use of proper technique and compliance to the study schedule, also monitoring any adverse events (Fig.1). The devices (tDCS & sham tDCS) will be programmed and cannot be tampered. Participants will be assessed at baseline,

[figure not shown]
[figure not shown]

Fig. 1 Illustrative image of home-based tDCS.

treatment day 14, treatment day 28, treatment day 42, and 6 weeks post-treatment (Fig. 2). The device will be returned in person at the end of the treatment (week 6).

Fig. 2 Proposed outline of the study.

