
sham tDCS), and specified outcome variables (e.g., Apathy) via traditional statistical tests (e.g., chi-square; Mann-Whitney; *t*-tests). Any sample characteristic variables that demonstrate a relationship with both predictor and outcome variables in a given model meet criteria for being a potential confounder (32, 33) and will be included as a covariate in such models for hypothesis testing.

Statistical modeling will primarily use generalized linear modeling (GLM) with multilevel components (GLMM) for correlated observations. Potentially nonlinear relationships between predictors and outcomes will be evaluated via inclusion of polynomial or spline effects. Continuous, dichotomous, and count-distributed data will utilize linear, logistic, and Poisson/negative binomial regression, respectively (each with a canonical link function). Evaluation of distributional assumptions will use residual plots, formal statistical tests, and posterior predictive checking. Violations of assumptions will be addressed via transformation, robust estimation, stratification, and/or coefficient scaling where appropriate. Statistical analyses will be performed using the R statistical computing environment via packages lme, rstan, and brms.

Missing data will be addressed via maximum likelihood, explicit modeling of missingness, or imputation where appropriate. Each approach is robust to ignorable missingness (i.e. MCAR and MAR). Sensitivity analyses will permit evaluation of the robustness of findings to missing data assumptions. While Bayesian analyses are not influenced by traditional concerns of multiplicity, for the frequentist analyses, all primary outcome variables (those specified by name in the hypothesis statements) will be evaluated at the $\alpha = 0.05$ statistical significance level, while any secondary or otherwise post hoc analyses will employ false discovery rate (FDR) to control for Type I error.

Study Population

We will randomize 40 patients aged 60 or older with ADRD and apathy to either active home-based daily (Monday to Friday) tDCS or sham tDCS for 6 weeks (1:1 for two groups). This sample size is set to maximize the number of participants that may be enrolled over the time period of the proposal assuming a credible average recruitment rate, given the financial parameters of the funding mechanism.

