The sample of this study consists of 40 older adults aged 60 years-old and over with ADRD and apathy. Study participants or their legally authorized representatives will give informed consent. Moreover, caregivers and/or relatives will be required to be present during the clinical assessments and tDCS sessions to ensure reliable information and proper use of the device. Participants will be recruited without any specific regard to sex, race, religion or ethnicity. Patients will be recruited at the UTHealth Geriatric Neuropsychiatry Clinic, the HCPC, and UTHealth Center for Healthy Aging. We will recruit ADRD patients whose dementia is of mild to moderate severity (~~CDR 1 and 2~~). Adults

younger than 60, adolescents and children are excluded as we are focusing on dementia, an age-related disorder that usually affects individuals aged 60 and older. No other special classes of vulnerable individuals will be included. It is anticipated that the subject demographic profile will mirror the larger population of individuals with ADRD from which they are recruited.

Informed Consent and Assent. Potential subjects and their caregivers/relatives will be informed about the study purpose, procedures, risks and benefits. They will be informed that participation in the research study is voluntary and that they are free to decline to be in the study, or to withdraw from it at any point. Study records will be kept confidential. Study information will be coded, and only study personnel will have access to the files.

Protection Against Potential Risks. The risks to the subjects involved in this study are minimal. To ensure this, we will take necessary steps to reduce risk for all study participants. We will try to create an atmosphere of security and trust prior any clinical assessment in order to minimize any discomfort with the research questions. In addition, subjects are always given permission to not answer questions with which they feel uncomfortable. A number of procedures (e.g. use of identifying numbers instead of names) will be implemented to protect subjects against loss of confidentiality. Side effects related to active tDCS application are uncommon, and mild when present, including: itching and burning sensation on the scalp, mild headache, dizziness, and fatigue. No serious adverse effects have been reported with tDCS.

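### The plan does not say whether participants who stop stimulation early are still assessed at weeks 6 and 12, and the main apathy model leaves out their week-2 and week-4 scores

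*Combined protocol and SAP*

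**What the plan says.** **Main model.** Study Procedures says that "GLM will evaluate residual change by modeling apathy at the end of treatment as a function of treatment group", controlling for the starting score. The secondary clinical outcomes are modelled the same way. Change over time by mixed model (GLMM) is a follow-up analysis.

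**Visit dates.** Study Procedures has apathy "assessed at baseline, during treatment (weeks 2, 4 and 6) and 6 weeks post-treatment". Study Design lists "treatment day 14, treatment day 28, treatment day 42, and 6 weeks post-treatment" after baseline, and the General Information table agrees. Study Design also places the return of the device at the end of treatment and identifies that as week 6. Table 1 ("Timetable for Collection of Data") marks AES at baseline and at weeks 2, 4, 6 and 12, without conditions.

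**Leaving.** Under Informed Consent and Assent, participants are told "they are free to decline to be in the study, or to withdraw from it at any point". Nothing describes stopping stimulation while remaining in follow-up.

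**Incomplete data.** Study Procedures expects more than 70% to complete and plans a comparison of completion rates between arms. The statistics text says: "Missing data will be addressed via maximum likelihood, explicit modeling of missingness, or imputation where appropriate". It describes these approaches as robust to ignorable missingness and promises sensitivity analyses without specifying them.

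**The concern.** Dates counted from treatment and dates counted from the calendar agree only for a participant who takes the full course. Suppose a caregiver stops the sessions in week 3. Table 1 points to AES at weeks 6 and 12. Counting six weeks after treatment could mean week 9. Nothing says which applies, or whether the visits continue. The AES is answered by the caregiver and does not need the device, so the score can still be obtained if someone is told to ask for it.

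The main model adds to the problem. It needs a baseline score and one end-of-treatment score. A participant with AES at baseline, week 2 and week 4 but not week 6 gives it no outcome unless an imputation, not yet specified, supplies one.

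Stopping may be related to tolerability, to lack of benefit or to caregiver burden. If sites resolve the gap differently, the efficacy comparison could lose some randomised participants or mix scores taken at different times. An uncollected week-6 score cannot be recovered at analysis.

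**Working it through.** **1. The plan's own power figure.** Inputs from Statistics: N = 40, alpha 0.05, Cohen's f = 0.45, stated power 80%. Use the noncentral F for two groups and one covariate, with df1 = 1, df2 = N − 3 and noncentrality f²N.

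- N = 40: df2 = 37, noncentrality 0.2025 × 40 = 8.1, power **79.1%**. The stated figure reproduces, provided all 40 have an outcome in the model.

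**2. How many might be affected.** More than 70% of 40 is more than 28, so at least 29 completers and at most 40 − 29 = **11** non-completers. This is a ceiling for the week-6 score: the study period is 12 weeks, and a participant lost after week 6 is a non-completer who has that score.

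**3. Power if non-completers are simply absent** (f = 0.45 unchanged):

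| Analysed | Power |
|---|---|
| 36 | 74.6% |
| 32 | 69.2% |
| 29 | 64.6% |
| 28 (the 70% boundary) | 62.9% |

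**4. Power if all 40 are scored at week 6, including those off stimulation.** For two equal groups d = 2f = 0.90. Assume a share s of the active arm stops and keeps a fraction r of the effect. Then:

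- mean difference = 0.90 × [(1 − s) + s·r]
- active-arm variance = 1 + s(1 − s)[0.90(1 − r)]²; sham variance = 1

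Example, s = 0.20 and r = 0: difference 0.72; active variance 1 + 0.16 × 0.81 = 1.1296; pooled SD √1.0648 = 1.032; f = 0.72 / (2 × 1.032) = 0.349; noncentrality 40 × 0.349² ≈ 4.87; power **57.5%**.

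| Stopping in active arm | Keep all | Keep half | Keep none |
|---|---|---|---|
| 10% | 79.1% | 74.6% | 68.8% |
| 20% | 79.1% | 69.7% | 57.5% |
| 30% | 79.1% | 64.5% | 46.1% |

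The values of s and r are assumptions. Steps 3 and 4 estimate different quantities, so a higher figure in step 3 is not an argument for dropping stoppers. Following everyone can give lower power than analysing completers.

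**5. Size of a possible bias (hypothetical).** Suppose stoppers' week-6 AES would be D points worse than that of those who stay, with 30% stopping on active and 10% on sham (6 + 2 = 8 of 40). An unadjusted completers-only difference is then shifted towards active tDCS by (0.30 − 0.10) × D = 0.2D: 0.6, 1.0 and 1.6 points for D = 3, 5 and 8. The documents give neither D, nor the split, nor an AES standard deviation, so these points cannot be put on a standardised scale.

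**The case against.** A reader might infer that early stoppers will have no comparable AES at weeks 6 and 12 and will be treated as dropouts. The documents do not support that. Study Design dates the end of treatment as week 6, Study Procedures names weeks 2, 4 and 6, and Table 1 lists AES at weeks 6 and 12 without conditions. No passage ends assessments when stimulation stops. The sentence on withdrawal is a general statement of voluntary participation and does not equate stopping sessions with leaving the study. Consent forms, which are not in the text reviewed, may say more. The natural reading for most participants is a fixed week-6 endpoint.

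A reader might also infer that the analysis is biased towards active tDCS. That is not shown. The plan adjusts for baseline, allows imputation and explicit modelling of missingness, promises sensitivity analyses, and compares completion between arms. It describes side effects as uncommon and mild, and sham also begins with current, so arm-related stopping is possible but not established.

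These points remove the stronger claims, but not the gap. No sentence tells staff to keep assessing someone who has stopped, or dates the last visit for that person. Imputation and maximum likelihood do not collect the score, and the sensitivity analyses are not said to cover non-ignorable loss. The model that would use the week-2 and week-4 scores is not the main one.

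**Conclusion.** The concern holds as a gap in definition and data collection. The week-6 and week-12 AES of participants who stop early is undefined in the plan, not excluded by it. The main model also makes no direct use of interim AES from anyone lacking the week-6 score.

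Up to 11 of 40 may not complete the 12-week study, on the plan's own expectation; the number without a week-6 AES may be smaller. No bias can be estimated from the documents, because the 0.2D figure rests on assumed inputs and an analysis that the plan does not commit to.

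Closing the gap yields a comparison of randomised arms at one stated time. It does not promise more power. Feasibility, acceptability and safety are the primary goal and efficacy is secondary, so the severity is moderate: the change should be made, and it is cheap if made before data are lost.

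**What to change.** The change concerns data collection and analysis only.

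- Define the AES endpoint as week 6, and follow-up as week 12, both counted from randomisation, for every randomised participant. Align the wording in General Information, Study Design, Study Procedures and Table 1.
- State that stopping stimulation is not the same as leaving the study. Ask those who stop to keep the Table 1 assessments unless they withdraw consent to data collection. Record the two events separately, which also makes the completion rate easier to interpret.
- Analyse by randomised arm.
- Take the week-6 contrast, in both the Bayesian and frequentist analyses, from the planned GLMM with baseline adjustment and AES at weeks 2, 4 and 6. NPI-Q and bDAS can be handled the same way; MMSE and the Cornell scale have no week-2 or week-4 scores to add.
- Specify that the promised missing-data sensitivity analyses include non-ignorable loss.

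**Cost.** Protocol and consent wording, and a few more caregiver interviews within the five assessments already compensated. Scores taken off stimulation can dilute the estimated effect, possibly materially, as step 4 of the working shows. That should be stated openly when the target of estimation is chosen.
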